6.3.4 Exposure to COVID-19 patients

The following household characteristics of subjects included in the study will be descriptively summarized for HCWs with and without COVID-19 infection (see Table 8.2.5 in the appendix):

- Contact with confirmed COVID-19 patients (Yes; No)
- Direct care to COVID-19 patients (Yes; No)
- Face-to-face contact (within 1 metre) of COVID-19 patients (Yes; No)

- Present when aerosol generating procedures performed (Yes; No)
- Average number of COVID-19 patients in contact each week for past month
- Number of days spent at work in last week
- Number of hours worked directly with COVID-19 patients in last week

For HCWs with COVID-19 at entry: responses to the baseline survey will be used.

For HCWs with COVID-19 at follow-up: maximum responses over the entire follow-up time available in the data cut. In addition, maximum responses in the 2 or 4 weeks (TBD) prior to COVID-19 infection date will be described.

For HCWs with no COVID-19 infection at any time: maximum responses over the entire follow-up time available in the data cut. In addition, maximum responses in the 2 or 4 weeks (TBD) prior to the data cut date will be described.

Maximum responses will be defined as:

- For a yes/no question, “yes” will be considered
- For number of days spent at work and number of hours worked directly with the COVID-19 patients, a summation will be done
- For average number of COVID-19 patients in contact each week for past month, an average will be calculated

Using the follow-up survey data for questions with yes/no responses, the following plot will be generated to display exposure over time:

For,

i = question #

n_{it} = # of yes answers to question i at time t

n_t = # of responders at time t

$$r_t = \sum_i n_{it}/n_t$$

A line plot of r over time will then be displayed. Two separate lines will be generated, one for HCWs infected with COVID-19 and another for HCWs that were never infected with COVID-19.

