6.3.7 Prophylactic medications

Prophylaxis usage of subjects included in the study will be descriptively summarized for HCWs with and without COVID-19 infection (see Table 8.2.8 in the appendix):

A stacked bar chart will be used to display the prophylaxis usage during the follow-up period. The x-axis will be dates of survey responses and the stacked bars will be grouped by yes/no (corresponding to prophylaxis use at specific dates). This will be done separately for HCWs infected with COVID-19 and those uninfected. The stacked bar charts can be used to compare prophylaxis use among infected/uninfected HCWs over time. This will be done for “any prophylaxis use” and if sample if sample sizes permit they will

be presented for the major individual prophylaxis treatments (ie. azithromycin, chloroquine/hydroxychloroquine, ivermectin, lopanavir).

Prophylaxis usage pre- and post- first date of COVID-19 exposure will also be described, stratified further by COVID-19 infection status.

- Types, intake frequency, and doses of prophylactic treatments
 - Treatment name
 - Date started
 - Date stopped
 - Dose (intake)
 - Duration of treatment
 - Dose frequency and dosing interval
 - Status (stopped/ongoing)
 - Reason for stopping (not available/side effects/expense/other)
 - Number of missed doses and reason (not available/side effects/expense/other)

For HCWs with COVID-19 at entry: prophylaxis treatments used before the COVID-19 infection date will be described.

For HCWs with COVID-19 at follow-up: prophylaxis treatments used over the entire follow-up time available in the data cut. In addition, prophylaxis treatments used within 2 or 4 weeks (TBD) before COVID-19 infection date will be described.

For HCWs with no COVID-19 infection at any time: prophylaxis treatments used over the entire follow-up time available in the data cut. In addition, prophylaxis treatments used within 2 or 4 weeks (TBD) prior to the data cut date will be described.

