6.4 Primary analysis

6.4.1 Frailty model: mixed effect Cox regression

For the time to COVID-19 infection outcome, both crude and adjusted hazards ratios will be estimated for time to COVID-19 infection with respect to prophylaxis use. The primary objective of this analysis is to assess the association between prophylactic treatments and the reduced risk of SARS-CoV-2 infection in HCWs caring for COVID-19 patients. A mixed effect Cox regression model (ie. frailty model) will be used to estimate adjusted hazard ratios. This method will allow the utilization of both the repeated measures gathered from each HCWs surveys, as well as the incorporation of time-varying covariates of interest such as PPE usage and COVID-19 exposure. Each subject will be included as a random effect. Both time-fixed and time-varying covariates will be included in the model. Covariates will be assessed using a univariate model, any covariates with a p-value less than 0.20 will be included in a multivariate model. A backward stepwise process will then be completed, where the covariates with largest p-value are removed one at a time until all covariates that remain are significant at the 0.10 level. The time-fixed covariates, healthcare facility and country will be included in the model regardless of their significance level. Including the healthcare facility and country covariates will make each healthcare worker's COVID-19 outcome conditionally independent on the background COVID-19 incidence occurring within each subject's healthcare facility and country. A list of additional covariates to be considered can be found in Table 5.4.1. For each subject in the control group, the index date (ie. time of first known exposure to COVID-19 patients) will be used as time zero. For HCWs that are treated with prophylaxis at any time their index date will be 7 days after initiation of treatment. Having an index date near treatment initiation will prevent the introduction of survivorship bias into the analysis.

Table 5.4.1 Model Covariates

Time-fixed/Time-varying Covariate	Covariate Name
Time-fixed Covariates	Healthcare facility, Country, Age, Biological Gender, BMI, Smoking status, Ethnicity, Blood type, Primary work location, Type of healthcare worker, Medical history

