Time-varying Covariates	Others in household exposed to COVID-19 infected individuals, Others in household showing symptoms of COVID-19, Others in household diagnosed with COVID-19, Number of COVID-19 infected patients exposed to, Direct care to COVID-19 patients, Face-to-face contact of COVID-19 patients, Present when aerosol generating procedures performed, Mask usage, Gown usage, Eye protection usage, Glove usage
-------------------------	--

Note: The necessity to create composite variables or collapse categories within variables will be determined upon the completion of the descriptive analyses. A correlation analysis will be completed to assess the level of correlation between variables, if a high level of correlation is found only one of the variables will be included as a covariate in the models.

A Cox model with mixed effects can be formulated as $h_i(t) = h_0(t) \exp(\mathbf{X}_i B + \alpha_j)$, where α_j denotes the random effect associated with the j -th cluster. The random effect can be thought of as a random intercept that modifies the linear predictor, while the shared frailty term has a multiplicative effect on the baseline hazard function: $h_i(t) = h_0(t) \exp(\alpha_j) \exp(\mathbf{X}_j B)^3$.

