6.5 Secondary analysis

All time-to-event secondary analyses will be conducted similarly as for the primary analysis. They include:

- Time to clinical events (each defined by the WHO severity score or proxies to be defined)
 - Ambulatory status with no limitation of activities (WHO Ordinal Scale classification 1). This will be defined as subjects reporting COVID-19 related symptoms, clinical diagnosis of COVID-19 or positive test results, but reporting “No” limitation of activities due to their symptoms and no hospitalisation.
 - Ambulatory status with limitation of activities (WHO Ordinal Scale classification 2). This will be defined as subjects reporting COVID-19 symptoms, clinical diagnosis of COVID-19 or positive test results and reporting “Yes” to having their usual activities limited being limited due to their symptoms, but no hospitalisation.
 - Hospitalised mild disease (WHO Ordinal Scale classifications 3 and 4). This is defined as being hospitalised without being admitted to the ICU or without ventilation.
 - Hospitalised severe disease (WHO Ordinal Scale classifications 5 to 7). This is defined as being hospitalised with either admittance to the ICU and/or receiving ventilation.
 - Death (WHO Ordinal Scale classification 8)

Furthermore, to explore key factors (eg. PPE, HCW and healthcare facility characteristics, underlying co-morbidities, household history and COVID-19 exposure) that potentially modify the risk of COVID-

19 among HCWs, the following analysis will be undertaken. For the covariates remaining in the final model of the primary analysis, one covariate will be removed at a time and will be tested using a likelihood ratio test to determine their association with the primary outcome.

Finally, as described in section 3.5.2, the type of prophylactic treatments (Chloroquine, Hydroxychloroquine, Azithromycin, Lopinavir/ritonavir, Ivermectin, others) will be characterized by dose, frequency and duration, overall and by country/region/site. To note, prophylactic treatment use will be defined by relevant indication from 'prophylactic treatment' section of the survey; in addition, if there is an indication of drugs in 'concomitant medications' section that are also listed but not selected under 'prophylactic treatment' section, those indications will be added too.

Other derived variables such as time in hospitalization will be analyzed via generalized mixed effect models.

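### SAP 6.4.1 gives each HCW a random effect because surveys repeat, but if infection counts once per HCW the frailty variance is poorly determined and can shift the reported hazard ratio

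*SAP*

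**What the plan says.** SAP 6.4.1 specifies a frailty model for time to infection. It states "Each subject will be included as a random effect" and gives as one reason "This method will allow the utilization of both the repeated measures gathered from each HCWs surveys"; the other is the use of time-varying covariates. Facility and country are forced in as covariates, so the HCW is the only random effect named. The formula that follows is generic: its random-effect term "denotes the random effect associated with the j -th cluster".

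The SAP does not say whether an HCW can contribute more than one infection. Three features imply that each contributes at most one:

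- One infection date serves as the reference point, in SAP 6.3.4 ("prior to COVID-19 infection date will be described") and 6.3.7 ("prophylaxis treatments used before the COVID-19 infection date will be described").
- The exposure plot in 6.3.4 has one line for infected HCWs and "another for HCWs that were never infected with COVID-19". Shell Table 8.2.1 likewise sorts HCWs into infected at baseline, infected during follow-up, or uninfected.
- There is no rule for re-entering the risk set after an infection.

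SAP 6.5 adds that "All time-to-event secondary analyses will be conducted similarly as for the primary analysis", and its list includes death. Protocol 8.7.4, in contrast, plans repeated time-to-event analyses that account for clustering within subject. SAP 6.4.1 keeps the subject term but defines no repeat event.

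**The concern.** A subject random effect has a clear role when a subject can have several events: events within a person are correlated, and the variance can be estimated from that correlation. With at most one event per person no such correlation is observed. Weekly covariate updates do not supply it, because in start-stop form each HCW's rows still end in at most one event.

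The model then learns the frailty variance only from the shape of the hazards. If hazard ratios between groups shrink over follow-up, a frailty model can read this as depletion of frail people and enlarge the covariate effects in response. The SAP names no frailty distribution. It also plans no proportional-hazards check, no report of the variance and no analysis without the term, so a reader could not see how far the estimate had moved. At stake is the size of the primary hazard ratio, to which SAP 6.7 attaches a fallback analysis when it is 0.8 or less without significance.

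**Working it through.** **Inputs from the documents** (protocol 8.7.7; SAP 5, 6.1, 3.4): N = 10,000; 20% unexposed; risk 10% in the unexposed; relative risk 0.78; two-sided 5%; 12 weeks. Risk in the exposed is 0.78 × 10% = 7.8%. Expected infections are 2,000 × 0.10 + 8,000 × 0.078 = 824.

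**The plan's own figure.** With the Schoenfeld formula, SE(log HR) = 1/√(824 × 0.2 × 0.8) = 0.087. Power is Φ(0.2485/0.0871 − 1.96) = 81%, which reproduces the stated 80%. (A pooled two-proportion formula gives 87.7%.) The frailty question does not touch this figure.

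**Same risks, different hazard ratio.** Under gamma frailty with variance θ, the conditional hazard ratio implied by risks p0 and p1 is

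HR = [(1 − p1)^(−θ) − 1] / [(1 − p0)^(−θ) − 1], and log(1 − p1)/log(1 − p0) at θ = 0.

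| θ | Calculation | HR |
|---|---|---|
| 0 | log 0.922 / log 0.9 | 0.771 |
| 1 | 0.0846 / 0.1111 | 0.761 |
| 4 | 0.3838 / 0.5242 | 0.732 |
| 6 | 0.6279 / 0.8817 | 0.712 |

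The two risks are identical in every row; only the assumed variance differs.

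**How well is θ determined?** Simulation with no person-level frailty: true HR 0.78, 80% exposed, 12 weekly intervals, about 820 events, at most one event per HCW, no other covariates. Assumptions not in the documents: 40 facilities of 250 HCWs as fixed terms, gamma form, facility log-hazard SD, and how facility hazards change over time. Shift is the HR without the subject term minus the HR with it.

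| Facility hazards | Median shift | Power with v without term | SAP 6.7 fallback newly met |
|---|---|---|---|
| Proportional | 0.000 (90th percentile 0.035) | 84% v 84% | 0% |
| Converging, SD 0.5 | 0.048 | 82% v 84% | 2.3% |
| Converging, SD 0.3 | 0.044 | 83% v 87% | 4.6% |
| Widening | 0 | – | 0% |
| Calendar waves, entry over 26 weeks | 0.001 (90th percentile 0.048) | – | 0.4% |

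Converging means that facility log-hazard differences halve over 12 weeks. The median fitted variance was then 6 at SD 0.5, although the true value was 0. Under proportional hazards the 10th to 90th percentile of the fitted variance was 0 to 3, and the shift reached 0.03 in 12% of studies.

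**With a covariate in the model.** Adding one three-level covariate to the converging setting cut the median shift to 0.024 (log-HR 0.5 per level) or 0.015 (1.0 per level). A separate calculation without facilities, 60 data sets per setting and no true frailty, gave a 5th to 95th percentile of fitted θ of 0 to 4.4 with such a covariate (0.5 per level) and 0 to 16.7 with none.

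**A second route.** With no frailty but a waning effect (HR 0.60 in weeks 1–6, 0.98 after), the plain model gives 0.78. The frailty model gives 0.75 with the covariate and about 0.52 without.

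**The reverse case, true frailty.** Take a conditional HR of 0.78 and control risk 10%. The control conditional cumulative hazard is H = (0.9^(−θ) − 1)/θ, and exposed survival is S1 = (1 + 0.78 θ H)^(−1/θ).

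- θ = 2: H = 0.1173, S1 = 0.9194, log S1 / log 0.9 = 0.797.
- θ = 4: H = 0.1310, S1 = 0.9179, log S1 / log 0.9 = 0.813.

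Without the term the HR is therefore about 0.02 to 0.03 closer to 1. A small simulation (150 studies per setting, so approximate) gave mean HRs of 0.81 without v 0.785 with the term at θ = 2, and 0.83 v 0.79 at θ = 4 with a covariate. In a further run of 120 studies per setting, root mean square error around 0.78 was no worse without the term in any of seven settings. Under true frailty it was 0.069 v 0.076 and 0.077 v 0.091 (without v with).

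**The case against.** **Real heterogeneity.** HCWs surely differ in ways that Table 5.4.1 does not capture, and then the subject term targets the conditional hazard ratio. This stands as a cost of removing the term: the estimate becomes a marginal one, and near the 0.8 cut-off in SAP 6.7 a difference of 0.02 to 0.03 could decide whether the fallback applies. It does not rescue the term, because the noise in the fitted variance cost at least as much accuracy as it gained.

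**Size.** Convergence of facility hazards is an assumption with no source in the documents. Protocol 8.2.3 describes open-ended enrollment, which is closer to the staggered-wave setting, where the median shift is 0.001. Table 5.4.1 lists many covariates, and these pin the variance down better. Sampling error is also larger: 0.78 × exp(±1.96 × 0.087) is about 0.66 to 0.93. All of this stands. A shift of 0.05 should not be read as the expected shift in the adjusted model.

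**One event is not stated.** Protocol 8.7.4 plans repeated events, the surveys collect symptoms and tests weekly, and SAP 6.6 repeats the primary analysis in HCWs who already had COVID-19 at entry. This also stands. If repeats count, the defect is the missing event definition, not the subject term.

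**Stronger readings to avoid.** A reader might infer that the variance is unidentified, or that the primary test is invalid. With covariates and a stated distribution the variance is identified, though weakly, and test verdicts differed between the models in at most 6.3% of simulated studies. A reader might also infer that the formula contradicts the text because it speaks of a cluster. It is a generic form, and the text names the subject, so there is no contradiction.

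**Conclusion.** The stated reason does not support a subject random effect for first infection, and it cannot support one for death. On the one-infection reading, the primary hazard ratio depends on a poorly determined variance. With no true frailty the typical shift is 0 under proportional facility hazards. Under assumed convergence it is about 0.05 with no other covariate and about 0.015 to 0.025 with one moderate or strong covariate. The issue is the reported effect size; test and power change little. It should be fixed, with medium confidence, because it concerns the primary estimate and the repair is cheap. The sizes rest on assumed facility numbers and spread, a gamma frailty, and exposure fixed in time.

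**What to change.** State in SAP 6.4.1 whether infection counts once per HCW.

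- **If once, and for death:** drop the subject random effect from the primary model. Fit a counting-process (start-stop) Cox model with the time-varying covariates, keep facility and country as 6.4.1 already requires, and check proportional hazards. A subject-frailty model may be reported as a sensitivity analysis, with its distribution and fitted variance stated.
- **If repeats count, as protocol 8.7.4 suggests:** define the recurrent event and the re-entry rule, name the frailty distribution, and keep the subject term for that analysis only.

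Stratifying by facility is an option, not part of the required change.

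The cost is SAP wording and one line explaining the departure from the subject-level clustering in protocol 8.7.4. No extra data are needed and the model is simpler to fit. The SAP should say that the resulting hazard ratio is marginal over unmeasured differences between HCWs, and so somewhat closer to 1 than a conditional one if those differences are large.

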2.2 Secondary objectives

- To characterize the type of potential prophylactic treatments, by dose and duration, overall, and by country/region/site.
- To explore the key factors (for example, use of PPE, HCW and healthcare facility characteristics, underlying co-morbidities, household history and COVID-19 exposure) modifying the risk of COVID-19 among HCWs.

[figure not shown]
3 Study overview

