3.1.1 Study population and setting

The study population comprises male and female HCWs, aged 18 years or older, working in healthcare facilities (e.g., acute care hospital) or in a community healthcare setting (e.g., clinic) in Indonesia, Kenya, Nigeria, Pakistan, Senegal, South Africa, Uganda, Zimbabwe, and Zambia. Hospitals or healthcare facilities directly participating in the study in target countries of interest should have at least five COVID-19 cases at the time of establishing the registry. Institutions that participate in the study should be able to provide a list of HCWs exposed to COVID-19 patients. As per the WHO definition², HCWs eligible for enrollment are limited, based on the high likelihood of being exposed to COVID-19 patients during patient care, to the following positions:

- Medical doctors*
- Clinical officers*
- Licensed physician assistant or nurse practitioner*
- Registered nurse (or equivalent)*
- Assistant nurse, nurse technician (or equivalent)*
- Phlebotomist
- Clinical pharmacist
- Clinical physical therapist
- Respiratory therapist
- Community healthcare worker

*These should include the following primary specialties:

- Surgery (all sub-specialties)
- Internal medicine (general)
- Pulmonology/critical care
- Emergency medicine

- Geriatrics
- Cardiology
- Infectious disease
- Anesthesiology
- Pediatrics
- Obstetrics/Midwifery
- Other

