3.6.5 Other Covariates

- COVID-19 symptoms (and date the symptoms begin)
 - Fever (temperature over 38°C)
 - Subjective fever (felt feverish)
 - Chills
 - Myalgia (muscles hurt or ache)
 - Rhinorrhea (runny or drippy nose)
 - Pharyngitis (sore throat)
 - Cough (new onset or worsening of chronic cough)
 - Dyspnea (hard to breathe or difficulty breathing)
 - Pneumonia
 - Nausea or vomiting
 - Headache or migraine
 - Abdominal pain (pain in tummy)
 - Asthenia (weakness or loss of strength)
 - Arthralgia (joint pain)
 - Anosmia (loss of smell)

- Ageusia (loss of taste)
- Blue coloring in toes
- Diarrhea (two or more looser-than-normal stools in 24 hours)
- SARS-CoV-2 testing
 - Type of test, if known
 - PCR (positive/negative)
 - Antigen test (positive/negative)
 - Serology (IgG and/or IgM, positive/negative or titer)
 - Date of test
- Household history (COVID-19)
 - Number of household contacts
 - Additional household member(s) exposed to COVID-19 (yes/no). If yes, how many
 - Additional household member(s) with symptoms consistent with COVID-19 (yes/no). If yes, how many?
 - Additional household member(s) diagnosed with COVID-19 (yes/no). If yes, how many
- Healthcare worker-level covariates
 - Demographics at entry
 - Underlying conditions and key comorbidities
 - Job characteristics
 - Concomitant medications
 - Blood type
- Healthcare facility characteristics
 - Country, region
 - Urban or rural setting
 - Type of facility (public/private/community healthcare)
 - Teaching/university hospital or non-teaching
 - Capacity
 - number of patients tested for COVID-19
 - number of COVID-19 patients treated
 - number of hospitalized beds (overall, ICU, emergency department)
 - number of exposed HCWs
 - number of HCWs tested for COVID-19
 - Number of HCWs who developed confirmed or clinically diagnosed COVID-19
 - Number of HCWs who died from COVID-19
 - Approved PPE use policy, and experience of PPE shortage
 - Approved prophylactic treatment policy
 - Shortage of COVID-19 related tests
 - BCG vaccination policy
- Concomitant medications (other than for COVID-19)
 - Antibiotics (yes/no). If yes, please specify.

- Azithromycin
- Trimethoprim/sulphamethoxazole
- Macrolide antibiotics (roxithromycin, clarithromycin, erythromycin)
- Other antibiotics
- Antimalarials (yes/no). If yes, please specify.
 - Hydroxychloroquine
 - Chloroquine
 - Sulfadoxine-pyrimethamine (SP)
 - Other antimalarials
- Antiparasitics (yes/no). If yes, please specify.
 - Ivermectin(yes/no)

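### Facility and country are both forced into the Cox model although facility determines country, and no facility characteristic gets a hazard ratio or test despite SAP 6.5

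*SAP*

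**What the plan says.** SAP 6.4.1 exempts two terms from p-value selection: "The time-fixed covariates, healthcare facility and country will be included in the model regardless of their significance level". The reason given is adjustment for background incidence: "Including the healthcare facility and country covariates will make each healthcare worker's COVID-19 outcome conditionally independent on the background COVID-19 incidence". The only random effect named is the HCW: "Each subject will be included as a random effect". Table 5.4.1 gives the time-fixed covariates as "Healthcare facility, Country, Age, Biological Gender, BMI, Smoking status, Ethnicity, Blood type, Primary work location, Type of healthcare worker, Medical history". The note under that table adds that where variables are highly correlated, only one will enter the models.

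SAP 3.6.5 lists "Country, region" first among the healthcare facility characteristics, and Protocol Table 2 collects it per facility. SAP 3.1.1 names nine countries: "Indonesia, Kenya, Nigeria, Pakistan, Senegal, South Africa, Uganda, Zimbabwe, and Zambia".

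The second secondary objective (SAP 2.2) covers "use of PPE, HCW and healthcare facility characteristics" among the factors that may modify risk. To address it, SAP 6.5 takes the covariates left in the final primary model: "one covariate will be removed at a time and will be tested using a likelihood ratio test". The facility characteristics themselves (setting, type, teaching status, beds, policies, shortages) appear in SAP 6.3.1, where they are described and linked to HCW data for context and bias assessment.

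**The concern.** There are two linked problems.

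First, country is fixed once facility is known. Fitting both as fixed effects gives a rank-deficient design, and software will drop or arbitrarily constrain some columns. Any country coefficients that survive are reference contrasts created by that choice. The SAP 6.5 test for country would compare two identical models.

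Second, SAP 6.5 presents its drop-one procedure as the way to explore facility characteristics, but the model it starts from contains none. Adding the once-collected ones beside facility indicators would fail for the same reason that country fails. At stake is a named part of a secondary objective and a model that can be programmed in only one way. The primary estimate is not at stake.

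**Working it through.** **Plan's own figures.** The documents give neither the number of facilities nor any model degrees of freedom, so there is no stated figure on this point to reproduce. F is therefore assumed at 9, 18, 45 and 90. The simulated fits take their setting from SAP section 5: N = 10,000, 20% unexposed, 10% baseline risk and an effect of 0.78. That statement reproduces adequately. Events = 2,000 × 0.10 + 8,000 × 0.078 = 824, and power = Φ(√(824 × 0.2 × 0.8) × |ln 0.78| − 1.96) = Φ(2.853 − 1.96) = 81.4%, against 80% stated.

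**Inputs for the check.** C = 9 countries (SAP 3.1.1); facility and country both fixed and time-constant (SAP 6.4.1); each HCW in one facility and each facility in one country (implied by the time-fixed label and by country being recorded at facility level); at least one facility per country.

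**Formulas.**
- Columns for facility plus country = (F−1) + (C−1).
- Rank = F−1, because each country indicator is the sum of its facilities' indicators.
- Redundant columns = C−1 = 8, for every F.
- Degrees of freedom for dropping country = (F−1) − (F−1) = 0.
- Degrees of freedom for dropping facility while country stays = (F−1) − (C−1) = F−9.

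**Rank of the design matrix.**

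| F (assumed) | Columns | Rank | Rank with 3 constant facility characteristics added | df, drop country | df, drop facility |
|---|---|---|---|---|---|
| 9 | 16 | 8 | 8 | 0 | 0 |
| 18 | 25 | 17 | 17 | 0 | 9 |
| 45 | 52 | 44 | 44 | 0 | 36 |
| 90 | 97 | 89 | 89 | 0 | 81 |

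Adding three constant characteristics never raises the rank. With the facility indicators removed, country plus the three has rank 8 + 3 = 11 for F of 18 or more, so they become estimable.

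**Simulated Cox fits.** The subject frailty was omitted, which does not change the rank of the fixed effects. Dropping country gave a likelihood ratio statistic of 0 on 0 df. Dropping facility gave 36.3 on 9 df at F = 18 and 93.8 on 36 df at F = 45; these sizes reflect the simulated facility effects, and only the df carry over. The prophylaxis hazard ratio with facility alone and with facility plus country was 0.712 and 0.712 at F = 18, and 0.762 and 0.762 at F = 45. This equality is algebraic, since both models span the same column space. The combined fit at F = 90 did not converge, so only its rank is used.

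**Which characteristics are constant.** Protocol Table 2 collects setting, facility type and teaching status once, before the study. Beds and other capacity counts, PPE policy and shortage, prophylaxis policy, test shortage and BCG policy are collected before and at the end. These could vary over time, but Table 5.4.1 does not list them as time-varying covariates.

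**The case against.** Several points on the other side are fair.

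- *The correlation rule may already remove country.* SAP 6.4.1 protects the two terms from removal on significance only, so the rule under Table 5.4.1 could still apply. This partly stands. However, the rule does not say which of the pair to keep, and the same section justifies having both, so the two instructions need reconciling.
- *Country and facility are there for adjustment.* This stands. The stated purpose is background incidence, and facility alone achieves it. The shell tables include no model-coefficient table, so misreading of country coefficients is a possibility and not something the plan invites.
- *The objective is exploratory and has other inputs.* Primary work location is in Table 5.4.1, SAP 6.3 plans weekly incidence by facility and country-stratified displays, and SAP 6.3.1 describes the facilities. This stands, but none of it gives a hazard ratio or test for a facility characteristic.
- *The gap is one of omission.* This stands: the immediate cause is that Table 5.4.1 lists no facility characteristic. Aliasing is why the once-collected ones cannot simply be added.

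A reader might go further and infer that the model cannot estimate facility effects, or that every facility characteristic is non-estimable. The documents do not support either. Within-country facility contrasts are estimable and have a joint test on F−9 df when F exceeds 9. Items collected at start and end need not be constant within a facility, and would escape full aliasing if coded as time-varying.

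**Conclusion.** The point holds as a specification fault affecting a secondary objective. With facility and country both fixed, country contributes 0 df, no separate country effect is identifiable, and the SAP 6.5 test for it is void. This is true for any number of facilities. As written, facility characteristics receive no hazard ratio and no test, only description, although SAP 6.5 says its procedure will explore them.

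It would be wrong to conclude that the primary result is compromised, since the prophylaxis hazard ratio is identical with or without country. It would also be too strong to say that the facility part of the objective goes wholly unanswered, because facility identity can be tested and the characteristics are summarised.

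The conclusion assumes one facility per HCW, one country per facility, and facility entered as fixed indicators, which follows from the subject being the only random effect named. The F values in the table are assumptions; the redundancy of 8 columns does not depend on them.

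**What to change.** 1. In SAP 6.4.1 and Table 5.4.1, keep facility in the primary model and drop country as redundant. Amend the background-incidence sentence to match, and say how the correlation rule applies to forced terms. The prophylaxis hazard ratio does not change. Dropping facility would then test all F−1 contrasts, country differences included; if the within-country test on F−9 df is wanted, compare the facility model with a country-only model.
2. In SAP 6.5, add one secondary Cox model for the risk-factor objective: facility as a random effect, country as a fixed effect, the named collected facility characteristics, and the HCW covariates. Report hazard ratios with 95% confidence intervals. State whether items collected at start and end enter as baseline or time-varying values. Use this model only for facility and country factors, and not for the prophylaxis hazard ratio.

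The cost is SAP text and one extra model on data already collected. The downside is precision: after country is fitted, only F−9 contrasts between facilities carry information on constant facility characteristics (9 at an assumed F = 18, 36 at F = 45), so intervals may be wide. The number of facilities should be stated. Stratifying the baseline hazard by facility in the primary model is an option but is not required.
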